All statistical analyses will be conducted using IBM SPSS Statistics version 28.0 (IBM Corp., Armonk, NY, USA). Statistical significance will be set at a two-sided $p < 0.05$. Continuous variables will be presented as mean and standard deviation (SD) or median and interquartile range (IQR) where appropriate, while categorical variables will be summarized as frequencies and percentages.

Analyses will follow the intention-to-treat (ITT) principle, including all participants as randomized regardless of protocol adherence. A per-protocol analysis may also be conducted as a sensitivity analysis.

Study Design Considerations (Crossover Structure)

This study adopts a two-period, two-sequence crossover randomized controlled design:

Sequence A: VR CAVE → Simulated Home

Sequence B: Simulated Home → VR CAVE

Each participant serves as their own control, improving statistical efficiency and reducing between-subject variability.

Key effects to be evaluated include:

Intervention (VR CAVE vs simulated home)

Period effect (first vs second session)

Sequence effect (order of intervention)

Carryover effect (residual effect from first intervention)

Outcome Measures

Primary outcomes:

Clinical competence (CCQ total and subscale scores)

Self-confidence and satisfaction (SSS scores)

Cultural competence (CCA total and subscale scores)

All outcomes are treated as continuous variables.

Baseline Analysis

Baseline characteristics (e.g., gender, prior clinical experience) will be compared between the two randomized sequences:

Categorical variables: Chi-square test or Fisher's exact test

Continuous variables: Independent samples t-test or Mann-Whitney U test (if non-normal)

This step assesses the success of randomization.

Primary Analysis

A linear mixed-effects model (LMM) will be used to evaluate intervention effects while accounting for repeated measures and crossover design.

Model specification:

Random effect: Participant ID

Fixed effects:

Intervention (VR CAVE vs simulated home)

Period (1 vs 2)

Sequence (A vs B)

Time (pre vs post)

Interaction terms (e.g., intervention \times time)

The primary parameter of interest is the intervention effect, estimated as the difference in outcome scores between VR CAVE and simulated home conditions.

Carryover Effect Assessment

To assess potential carryover effects:

A sequence effect will first be examined within the mixed model.

Additionally, an interaction term (intervention \times period) may be explored.

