If a statistically significant carryover effect is detected ($p < 0.05$), analysis will be restricted to first-period data only, effectively treating the study as a parallel-group trial.

Within-Group and Between-Condition Comparisons

Pre–post changes within each condition will be analyzed using paired t-tests or equivalent model-based contrasts.

Between-condition differences (VR vs simulated home) will be derived from the mixed model estimates.

Handling Missing Data

Missing data will be assessed for patterns (missing completely at random, MCAR; missing at random, MAR).

Linear mixed models inherently accommodate missing data under MAR assumptions.

If necessary, multiple imputation will be performed as a sensitivity analysis.

Assumption Checking

Model assumptions will be evaluated:

Normality of residuals (Q-Q plots, Shapiro–Wilk test)

Homogeneity of variance

Linearity

If assumptions are violated, appropriate transformations or non-parametric alternatives will be considered.

Subgroup and Sensitivity Analyses

Where sample size permits, exploratory subgroup analyses may be conducted based on:

Prior clinical experience

Gender

Baseline competency levels

Sensitivity analyses:

Per-protocol analysis

First-period-only analysis (if carryover is present)

Effect Size Reporting

Effect sizes will be reported alongside p-values:

Mean differences with 95% confidence intervals (CI)

Standardized effect sizes (e.g., Cohen's d) where appropriate

Software and Reproducibility

All analyses will be conducted using SPSS v28. Syntax files and anonymized datasets will be retained to ensure reproducibility and auditability.

Project Plan

This project consists of the following four phases: 1) Preparatory phase -Developing two sets of VR CAVE community scenarios; 2) Briefing sessions; 3) Implementing the VR CAVE scenarios; and 4) Data analysis and generating design principles for VR CAVE model for community health nursing.

Phase 1: Preparatory phase

- Obtain HKU/HA HKW IRB.
- Inform and seek advice from Director of BN(FT) Program about the implementation of the project.
- Seek approval on using IAPCC-SV.
- Developing two sets of VR CAVE community scenarios

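### A carryover test decides whether the crossover or a Lab 1-only analysis is reported; if score levels are compared, the two-sided error is about 6% to 9%, not 5%

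*Combined protocol and SAP*

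**What the plan says.** The SAP, Study Design Considerations: "This study adopts a two-period, two-sequence crossover randomized controlled design". Under Primary Analysis, a mixed model with a random student effect has fixed effects for intervention, period, sequence, time (pre or post) and interactions such as intervention by time. The primary parameter is worded as a difference in scores between the two conditions, with no statement whether that means levels or pre-post change.

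Under Carryover Effect Assessment: "A sequence effect will first be examined within the mixed model". As a second look, "an interaction term (intervention \times period) may be explored". If carryover is significant at 0.05, "analysis will be restricted to first-period data only, effectively treating the study as a parallel-group trial".

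Under Subgroup and Sensitivity Analyses, the same analysis appears with a different status: "First-period-only analysis (if carryover is present)".

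The protocol, Phase 3, has all three instruments completed before and after each lab. Phase 4 gives another mixed model, with group by time but with no period term and no carryover rule.

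**The concern.** The sequence test and a first-period comparison of levels both compare the same two groups of students. A chance difference between the groups that makes the sequence term significant therefore tends to make the Lab 1 comparison significant too. The rule would then move to the less reliable analysis in just those trials where it is most likely to mislead.

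The trigger is also poorly aimed. The sequence term averages four scores, one of which, the Lab 1 pre-test, is taken before any session and cannot carry anything over.

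At stake are the stated 5% level, the Lab 2 data, and the within-student comparison that the SAP gives as the reason for a crossover.

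**Working it through.** **Inputs from the plan.** Two-sided 0.05 for the effect and for the carryover test; two sequences, two periods; four scores per student; a random effect for student only; 220 students invited. The plan gives no sample size, power or overall error rate, so there is no figure of its own to reproduce.

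**Assumed.** Score SD 1; equal correlation r between any two scores of a student (what a random intercept implies), r from 0.3 to 0.9; 110 students per sequence; no dropout.

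**1. Error of the two-stage rule, with no effect and no carryover.** The sequence contrast compares four-score means, each with variance (1 + 3r)/4. Its correlation with the Lab 1 comparison is:
- Lab 1 post-test: √((1 + 3r)/4)
- Lab 1 average of pre and post: √((1 + 3r)/(2(1 + r)))
- Lab 1 change: 0

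The crossover contrast is uncorrelated with the sequence contrast, so

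overall error = 0.95 × 0.05 + 0.05 × P,

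where P is the chance (bivariate normal) that the Lab 1 test is significant once the sequence test is. At r = 0.7 with post-tests: correlation √(3.1/4) = 0.880, P = 0.557, error = 0.0475 + 0.0279 = 0.075.

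| r | Post-test: P | Error | Pre/post average: P | Error | Change: error |
|---|---|---|---|---|---|
| 0.3 | 32% | 6.4% | 52% | 7.3% | 5.0% |
| 0.5 | 43% | 6.9% | 62% | 7.8% | 5.0% |
| 0.7 | 56% | 7.5% | 72% | 8.4% | 5.0% |
| 0.8 | 64% | 7.9% | 78% | 8.7% | 5.0% |
| 0.9 | 74% | 8.5% | 85% | 9.0% | 5.0% |

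If correlations decay with time (AR(1)), the two level readings give 6.3% to 8.5% and change stays at 5.0%. A first-period ANCOVA on the pre-test gives 5.1% to 5.8% over both structures. In simulation (60,000 trials per correlation, r from 0.5 to 0.9) the level readings gave 6.8% to 8.9%. With the switch removed they gave 4.8% to 5.1%.

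**2. Cost of an unneeded switch even on change scores.** At r = 0.7 the change within a lab has variance 2(1 − 0.7) = 0.6.
- Both labs: SE = ½√(2 × 1.2/110) = 0.074; power for 0.3 SD is 98%.
- Lab 1 only: SE = √(2 × 0.6/110) = 0.104; power is 82%.

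**3. What the sequence term measures.** Carryover c on both Lab 2 scores moves it by (c + c)/4 = c/2. At r = 0.7, the chance Lab 1 pre-test difference accounts for 0.880² = 77.5% of its variance.

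Take a difference of 0.3 SD that is fully retained, with 100 students per sequence and variance split into student / student-by-lab / residual. The sequence term shifts by 0.15 and has variance (student + half of student-by-lab + a quarter of residual). The Lab 2 minus Lab 1 pre-test difference shifts by 0.3 and has variance 2 × (student-by-lab + residual). SE = √(2 × variance/100).

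| Split | Sequence: variance | Power | Pre-test difference: variance | Power |
|---|---|---|---|---|
| 0.5/0.2/0.3 | 0.675 | 25% | 1.0 | 56% |
| 0.7/0.1/0.2 | 0.800 | 22% | 0.6 | 78% |
| 0.4/0.3/0.3 | 0.625 | 27% | 1.2 | 49% |

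Simulation agrees (22% to 26% and 48% to 78%).

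**4. A fixed change contrast under the same retention.** If a VR gain d is fully kept and the simulated home adds nothing, the four mean scores are 0, d, d, d (VR first) and 0, 0, 0, d (home first). VR change minus home change is d in both sequences. The post-test contrast is 0 in one and d in the other, so it averages d/2.

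**5. The second test.** Code intervention and period as ±1. In this design their product is the sequence indicator (up to sign). The design matrix with both terms has 7 columns and rank 6.

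**6. Three instruments.** If the rule runs separately on each and they were independent, at least one switches with probability 1 − 0.95³ = 14.3% when there is no carryover.

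**The case against.** **The effect may be meant as change.** The SAP names intervention by time as an interaction and analyses pre-post changes, and Phase 4 has group by time. With change in both stages the error is 5%. This stands: a reader might infer that the 5% level is certainly lost, and the documents do not support that. They leave the contrast open, and the loss follows only on the levels reading, which is the closest to the SAP's wording of the primary parameter.

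**The first-period analysis may be only a sensitivity analysis.** If that listing governed, the primary error rate would be untouched. But the carryover section states the restriction without qualification, so the two must be reconciled.

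**The sequence term does test carryover.** A reader might infer that it does not. Under randomisation its mean is zero without differential carryover (or an intervention-by-period interaction) and it moves when there is some. The fair description is diluted, low in power and non-specific.

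**Retained learning need not trigger the rule.** A reader might infer that the rule fires whenever teaching is retained. Retention that is equal after both settings goes into the period effect; only a difference in retention moves the sequence term.

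**The aliasing is minor.** The interaction is optional and can be fitted in place of sequence. That is correct; it is redundant, not a source of bias.

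**Change scores do not suit SSS.** Its items rate a simulation and how it was taught. Before Lab 1 there is none to rate, and before Lab 2 the natural object is Lab 1. This stands and limits the remedy.

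**Conclusion.** Wrong as written. The SAP lets a significance test choose between two analyses and gives the second of them two incompatible roles.

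On the levels reading the overall two-sided error is about 6% to 9% instead of 5%, and 32% to 85% of Lab 1 tests reached through the switch are false positives when there is no effect. On change scores in both stages it stays near 5%, and with a first-period ANCOVA it is about 5.1% to 5.8%. The SAP specifies neither. Even where the error holds, a chance imbalance can discard half the scores and the within-student comparison.

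The trigger would miss most differential carryover of 0.3 SD (power about 22% to 27%), while the pre-tests already planned would detect it more often (about 49% to 78%).

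These sizes rest on assumed correlations and variance splits, 200 to 220 students split equally, and no dropout. The 0.3 SD and full retention are illustrations, not figures from the plan.

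**What to change.** 1. Delete the switching rule.
2. Name one crossover contrast over both labs as primary, whatever the carryover result: pre-post change for CCQ and CCA, post-session scores for SSS.
3. Always report the Lab 1-only comparison as a sensitivity analysis, adjusted for the Lab 1 pre-test for CCQ and CCA. For SSS it is the main check on carryover, because no usable pre-test exists.
4. For CCQ and CCA, describe carryover by the between-sequence difference in the Lab 2 pre-test, adjusted for or minus the Lab 1 pre-test, with a 95% CI and no decision rule.
5. Drop the intervention-by-period term, and bring the Phase 4 model into line with the SAP.

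Cost: SAP wording and one table. No new data are needed.

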The principal investigator will conduct a separate briefing session before the intervention at a mutually convenient time. This session will ensure that they understand all logistics and the knowledge required to guide the students through the cases in the study.

All participants will have a pre briefing time before the start of scenario. The principal investigator will explain the nature, purpose, procedures, risks and benefits of the proposed project to potential participants. Confidentiality and the voluntary nature of participation will be emphasized. Students who agree to participate will sign a consent form. The principal investigator will provide briefings on the project logistics and student expectations to ensure they are fully informed.

Then, students will be asked to take a pre-test and post-test on knowledge, self-confidence, satisfaction, and cultural competence in community health nursing.

Phase 3: Implementing the VR CAVE model

In the second semester, the VR CAVE model will be applied with Year 5 nursing students in the Community & Global Health Nursing (NURS4604) course. Students will form groups and actively participate in conducting home assessments and identifying health hazards for the patient with a play time of 20 minutes. In the proposed study, fifth-year nursing students will interact with a VR CAVE, a virtual reality environment designed to simulate home visits for two unique patients, Stone Wong and May Wong, both situated in a poverty-stricken home setting (Figure 1). With around twenty hidden cues in each case, the VR CAVE provides a realistic and immersive environment that mirrors the patients' homes. These cues symbolize potential health risks and cultural preferences related to health, thus challenging the students to observe, assess, and respond effectively.

Prior to the intervention, an online Qualtrics e-consent will be obtained from the participants. Furthermore, a pre-test will be conducted using the Clinical Competence Questionnaire (CCQ), Student Satisfaction and Self-confidence in Learning (SSS), and Cultural Competence Assessment Instrument (CCA). This will allow us to measure the baseline competencies of the students before the intervention.

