The intervention group will then undergo the VR CAVE experience in Lab 1, while the control group will conduct a simulated home visit in the same lab. After completing the simulated home visit, the students will take an online Qualtrics post-test on the CCQ, CCA, and SSS. This will provide us with data to compare the competencies of the students post-intervention, and to assess the effectiveness of the VR CAVE as a training tool for nursing students.

Following the initial lab session, the two groups will switch settings for the second lab, thus ensuring a comprehensive and balanced assessment of the effects of the VR CAVE intervention.

The intervention group that initially experienced the VR CAVE will now shift to the

conventional simulated home, while the control group will have the opportunity to experience the VR CAVE intervention. This crossover design will provide a holistic view of the students' learning experience in both simulated environments.

Before the second lab session, participants will once again provide e-consent using Qualtrics. This reaffirms the ongoing voluntary nature of their participation. As in the first lab session, students will complete pre-tests using the Clinical Competence Questionnaire (CCQ), Student Satisfaction and Self-confidence in Learning (SSS), and Cultural Competence Assessment Instrument (CCA). This will allow us to monitor any changes in competencies as a result of the initial lab session.

After completing the second lab session, students will perform the same set of post-tests online via Qualtrics based on the CCQ, CCA, and SSS. This will enable us to evaluate any shifts in clinical, cultural, and satisfaction competencies following exposure to both the VR CAVE and the conventional simulated home. This comprehensive testing strategy will ensure that we capture a wide range of data to assess the overall effectiveness and impact of the VR CAVE technology in nursing education. The flow chart is shown in Figure 2.

Figure 1 VR CAVE model for poverty home

[figure not shown]

Figure 2 Flowchart of the study

Phase 4: Data analysis and generating design principles for a VR CAVE model

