The primary and secondary analyses will involve descriptive statistics, including mean and standard deviation, to summarize participants' demographics and scores from the Clinical Competence Questionnaire (CCQ), Cultural Competence Health Practitioner Assessment (CCHPA-129), and Student Satisfaction and Self-Confidence in Learning (SSS). Baseline characteristics of the intervention and control groups will be compared using the χ^2 test or Fisher's exact test for categorical data and the independent t-test for continuous data. The CCQ, CCHPA-129, and SSS scores will be evaluated using a linear mixed-model analysis. Participants will be included as the random effect with time, group, randomization sequence order, and group x time interaction as fixed effects. The analysis will adhere to the intention-to-treat principle,

conducted on subjects as randomized. All statistical analyses will be performed using IBM SPSS version 28.0. All statistical tests will be two-sided with the level of significance set at 0.05.

Design principles specific to the context of the VR CAVE will be generated based on the findings of this project. These design principles will guide and be applied in further designing and developing VR CAVE for community health nursing.

Project schedule

Phase	Estimated Completion Time
1: Preparatory phase	January 2025
2: Briefing session	February 2025
3: Implementing the VR CAVE model	April-August2025
4: Data analysis and generating design principles for a VR CAVE model phase	January 2026

Reference

1. Thompson, C. W., Moscola, S., & Buckland, S. T. (2021). Nursing student perceptions of home visit simulation scenarios. *Nursing education perspectives*, 42(2), 113-114.
3. Alıcı, N. K., & Emiroğlu, O. N. (2020). Students' home visit experiences within the scope of public health nursing course: A qualitative study. *Acıbadem Üniversitesi Sağlık Bilimleri Dergisi*, 12(1), 146-151.
4. Dalton, J. M., Aber, C., & Fawcett, J. (2009). Students' perceptions of home visiting. *Home Healthcare Now*, 27(4), 253-261.
5. Meeley, N. G. (2021). Undergraduate student nurses' experiences of their community placements. *Nurse Education Today*, 106, 105054.

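### The primary model has no term for the student groups that share a session, and states no residual covariance for the four scores per student

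*Combined protocol and SAP*

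**What the plan says.** Phase 3 describes the sessions as group work: "Students will form groups and actively participate in conducting home assessments and identifying health hazards for the patient". It also sets out the measurements. CCQ, SSS and CCA are completed before the first lab. After it, "the students will take an online Qualtrics post-test on the CCQ, CCA, and SSS". The three scales are repeated before the second lab, and after it "students will perform the same set of post-tests online via Qualtrics". Each student therefore has four scores per scale, two in each lab.

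The SAP (Primary Analysis) gives the random part of the model as "Random effect: Participant ID". Phase 4 gives the same structure: "Participants will be included as the random effect with time, group, randomization sequence order, and group x time interaction as fixed effects". In that sentence *group* is the study arm as a fixed effect, not the team of students.

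Neither place has a team term, a participant-by-lab term, a residual covariance structure or cluster-robust standard errors. The SAP defines the primary parameter as the intervention effect on outcome scores without naming a time point, and lists intervention by time only as an example of an interaction.

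The SAP also tests for carryover, first through the sequence effect. A significant result restricts the analysis to the first period.

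**The concern.** Students who search one home together for 20 minutes share that session. If the session goes well or badly for the whole group, their post-tests move together. A model with only a participant effect counts them as independent and credits the trial with more information than it has.

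The SSS is the scale most exposed, because its items (Appendix 2) ask about the session, the materials and the instructor.

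The second matter is the shape of the within-student correlation. Pre and post scores from one lab are likely to be closer to each other than scores from different labs. A participant intercept with independent residuals does not allow for this.

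At stake are the p-values and confidence intervals of all the primary outcomes, and the carryover decision that may discard the second period.

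**Working it through.** The plan states no sample size calculation, SD, ICC or power, so there is no figure of its own to reproduce. The documents supply the two-sided 5% level, the four scores per student in two labs, and 220 students invited (an invitation count, not an enrolment target). Group size, group stability, ICC and variance shares are assumptions. The flowchart (Figure 2) was not available to this review.

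**1. Groups.** Let m be the group size and ICC the correlation between group mates in the quantity analysed. The design effect is DE = 1 + (m − 1) × ICC, and the true type I error is 2 × [1 − Φ(1.96/√DE)].

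| m | ICC | DE | 220/DE | Type I error |
|---|---|---|---|---|
| 4 | 0.02 | 1 + 3 × 0.02 = 1.06 | 208 | 5.7% |
| 6 | 0.05 | 1 + 5 × 0.05 = 1.25 | 176 | 8.0% |
| 10 | 0.10 | 1 + 9 × 0.10 = 1.90 | 116 | 15.5% |

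A null simulation agrees. It used 4,000 runs, 220 students, 110 per sequence, total variance 1, participant share 0.5, and a group-by-session share of 0.02 to 0.10 acting on the post-test:

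| Test | Groups of 5 | Groups of 10 |
|---|---|---|
| Intervention by time | 6.0% to 9.4% | 7.4% to 15.3% |
| Intervention main effect | 5.9% to 10.0% | 7.6% to 16.6% |
| First-period fallback, change scores | 5.7% to 10.1% | 6.6% to 17.1% |

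A constant group effect (share 0.10) with groups kept together gave 4.7% for intervention by time and 5.5% for the main effect. It cancels within student.

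**2. Sequence test.** That constant effect does not cancel when sequences are compared. Take a group share g, participant share 0.5 − g and residual share 0.5. A student's mean of four scores has variance 0.5 + 0.5/4 = 0.625, so the ICC of the mean is g/0.625.

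- g = 0.02, m = 5: ICC 0.032, DE 1 + 4 × 0.032 = 1.128, type I error 6.5%.
- g = 0.10, m = 10: ICC 0.16, DE 1 + 9 × 0.16 = 2.44, type I error 21%.

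**3. Within-lab pairing, assuming independent residuals.** Let sp be the participant-by-lab share and se the residual share, with participant share 0.5, so se = 0.5 − sp. Within a student there are three degrees of freedom. One (between labs) has expected mean square se + 2sp and two have se. The fitted residual is therefore (3se + 2sp)/3 = se + (2/3)sp. The variance it should be set against depends on the contrast:

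- main effect averaged over pre and post: se + 2sp;
- post-test difference: se + sp;
- intervention by time: se.

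Type I error is 2 × [1 − Φ(1.96 × √(fitted/true))].

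| sp | Fitted | Main effect | Post-test difference | Intervention by time |
|---|---|---|---|---|
| 0.05 | 0.483 | true 0.55: 6.6% | true 0.50: 5.4% | true 0.45: 4.2% |
| 0.20 | 0.433 | true 0.70: 12.3% | true 0.50: 6.8% | true 0.30: 1.8% |
| 0.30 | 0.400 | true 0.80: 16.6% | true 0.50: 8.0% | true 0.20: 0.6% |

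Simulation at sp = 0.20 gave 12.3% for the main effect and 2.0% for intervention by time.

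**4. Both together.** With sp = 0.20 and a group-by-session share of 0.05 or 0.10 (groups of 5 or 10), simulation gave 15% to 24% for the main effect and 3.9% to 15.2% for intervention by time.

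**5. Effect of allowing for groups.** With groups kept together, analysing group means of the within-student contrast (first-lab change minus second-lab change) gave 4.2% to 5.8% in every scenario. The same contrast analysed by student, ignoring groups, gave 5.9% to 25% wherever a group-by-session effect was present.

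**The case against.** A reader might infer that the standard errors are plainly wrong and always too small. The documents do not support that, for five reasons.

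- **Covariance.** The residual covariance is unstated, not fixed as independent. Naming a participant random effect does not rule out a richer repeated-measures structure in SPSS, and the SAP says that the model is meant to handle the repeated measures. On this half the plan is under-specified rather than shown to be in error.
- **Contrast.** The largest covariance figures belong to an effect averaged over pre and post scores, which includes scores taken before the session. The plainer reading, a post-test difference, is only mildly affected (5.4% to 8.0%). Intervention by time is conservative unless a group effect offsets this.
- **Groups.** A stable effect of groups that stay together cancels in the within-student contrast. Only variation from session to session inflates that test.
- **Outcomes.** All outcomes are individual self-reports. Many CCQ items concern hospital procedures such as blood transfusion or tracheotomy care, which a shared home-visit session has little reason to shift. One ICC range for every scale is an assumption.
- **Setting.** The sentence on groups stands in the account of the VR CAVE. The text does not say that simulated-home students also work in groups. If they do not, the inflation would be smaller.

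All five stand and limit the claim. They do not remove it: no group term appears in either model, and no unstructured covariance within student would supply one.

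**Conclusion.** The point holds in a limited form. As written, the model ignores any group-by-session correlation, and intervals are too narrow to the extent that it exists. Under the assumed group sizes and ICCs, type I error is about 5.7% to 15.5%, with a similar range for the first-period fallback. With neither extra variance component the model is valid: simulation gave 5.4% and 5.2%.

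The covariance point is secondary and conditional on independent residuals. Its direction depends on the contrast, so the net direction of error cannot be settled until the plan says which contrast is primary.

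This should be fixed. Confidence is high that the group term is absent and moderate on the size, because group size, group stability, ICC and variance shares are all assumed.

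**What to change.** 1. Record each student's group in each lab, in the survey or, if collection is over (the schedule has Phase 3 in April to August 2025), from class records. State group size, whether groups stay together, whether both settings use groups, and whether students or groups are randomised.
2. Name one primary contrast.
3. Fit one of two models, with small-sample degrees of freedom:
   - one change score per lab, with fixed intervention, period and sequence, and random participant and group-by-lab session; or
   - the four-row model with an unstructured lab-by-time covariance within participant, plus a random group-by-lab effect on the post-test.
4. Carry the same group term into the sequence and carryover test and into the first-period fallback. If groups stay together, the sequence test also needs a constant group effect.

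The cost is one field per lab and a few lines of SPSS syntax. Intervals may be somewhat wider where groups matter. If group membership was never kept, the correction cannot be made and the limitation should be reported.
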